1.0 Study Summary

Study Title	Decreasing Antibiotic Duration for Skin and Soft Tissue Infections in Pediatric Primary Care Using Behavioral Economics Methods, A Cluster Randomized Trial
Study Design	Cluster, Randomized, Control
Primary Objective	Study the efficacy of a package of behavioral economics strategies (versus an education-only control condition) in altering clinician behavior regarding antibiotic prescription duration for skin and soft tissue infection (SSTI).
Secondary Objective(s)	Analyze patient and prescriber characteristics which affect long vs short duration of antibiotics for uncomplicated SSTI
Research Intervention(s)/Investigational Agent(s)	Behavioral economics package of Epic order panel with default treatment duration, plus accountable justification
IND/IDE #	n/a
Study Population	Primary care patients with diagnosis of SSTI and prescription for enteral antibiotics, NCH primary care providers, henceforth referred to as “clinician prescribers”
Sample Size	1000 patients (with SSTI encounters including 600 antibiotic prescriptions), 98 clinician prescribers
Study Duration for individual participants	12-16 months
Study Specific Abbreviations/Definitions	SSTI (skin and soft tissue infection), BE (behavioral economics), PCC (primary care clinics)

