2.0 Methods

2.1 The 14 NCH primary care clinics will be distributed into five geographic “regions.” Regions will be randomly assigned to the intervention condition or control condition. A region refers to a localized geographical zone within the greater Columbus area in which a NCH primary care pediatrician restricts her/his practice to a small number of clinics. All clinics (intervention and control) will receive baseline education regarding prescribing guidelines and release of a new Epic order panel. All 14 clinics will receive baseline education (control condition) about common infections and local and national guidelines for antibiotic choice and duration of treatment. Clinician prescribers will also be instructed about the presence of a new Epic order panel. The SSTI order panel will present itself when a clinician prescriber types in either a

NATIONWIDE CHILDREN'S HOSPITAL
SHORT PROTOCOL (Waiver of Consent or Verbal Consent)

PROTOCOL TITLE: SSTI BE in PC

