preferred drug name (cephalexin, clindamycin, TMP-SMX) or diagnosis (cellulitis, impetigo, etc). All clinician prescribers within primary care clinics will have access to these order panels, however the order panel will vary in functionality based on control vs intervention clinic. For control clinics, the order panel will include diagnosis and drug name only- antibiotic duration must be then determined by the clinician prescriber at the time of the visit. Within intervention clinics, the Epic order panel will include prepopulated default “short” duration antibiotic days based on diagnosis chosen. Short antibiotic duration is defined as 5 days or fewer for cellulitis or drained abscess and 7 days for impetigo or undrained abscess. This- full functionality, default short duration- order panel will only be released to intervention clinics. We hypothesize that clinics with the intervention will have higher rates of short course antibiotics for SSTI versus control clinics. In addition, those randomized to the study intervention sites will receive the following behavioral economic strategies: (1) Epic order panel for cellulitis, impetigo, and abscess with prepopulated duration fields regarding prescriptions; (2) accountable justifications to document reasoning (in a free text field) when the default duration is overridden; and (3) visual reminders placed in intervention clinics about the available Epic order panel. Encounter data for specific diagnosis codes with skin and soft tissue infections will then be collected and analyzed to include clinic location, patient demographics and presenting clinical characteristics, diagnoses, antibiotic treatment (name, dose, duration), and clinician prescriber names. Prescriptions for systemic antibiotics for the selected diagnoses will be reviewed and analyzed for rates of long and short course antibiotics. Rates of short and long antibiotics will be compared between the intervention and control groups.

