An education session (virtual via department meeting) will be provided at start of study to all clinics. The education session will include a succinct overview of current local and national treatment guidelines for SSTI. These guidelines include the 5-day and 7-day recommended durations mentioned in the previous paragraph. All clinics will be informed of the presence of order panel for diagnoses of interest. The information included in the order panel will vary based on whether a clinic resides in the control or intervention group. Control order panel will include only antibiotic names and doses. Intervention order panel will include default duration based on SSTI diagnosis.

For the secondary objective, patient demographic and clinical characteristics and clinician prescriber characteristics will be analyzed to determine which factors impact short versus long antibiotic treatment duration.

NATIONWIDE CHILDREN'S HOSPITAL
SHORT PROTOCOL (Waiver of Consent or Verbal Consent)

PROTOCOL TITLE: SSTI BE in PC

2.2 Clinician prescribers will provide prescriptions to patients for SSTI based on previously published national and local guidelines as well as prescriber preference/practice. Patients in primary care clinics receiving antibiotic prescriptions for SSTI will also serve as study subjects. No additional risks are incurred by subjects (clinician prescribers and patients) by participation in this study. For clinician prescribers in clinics randomized to the intervention group, use of the Epic order panel will be optional. Patients receiving care for SSTI in the NCH primary care clinics will receive no more than minimal risks as clinician prescribers will be providing treatment for SSTI as previously done, except for the optional use of the order panel. The study involves no direct interaction with clinic patients, and implementation of the BE interventions does not increase risks associated with treatment of SSTI.

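### Does calling the control education-only, when control clinics also receive an order panel, undermine the primary comparison?

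*Protocol*

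**What the plan says.** The Study Summary (Protocol, Section 1.0) states the primary objective as the efficacy of "a package of behavioral economics strategies (versus an education-only control condition"). The same table describes the intervention as a "Behavioral economics package of Epic order panel with default treatment duration, plus accountable justification".

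Section 2.1 sets out what each arm gets:

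- **Both arms.** "All clinics (intervention and control) will receive baseline education regarding prescribing guidelines and release of a new Epic order panel". The next mention of the education attaches the control label to it: "All 14 clinics will receive baseline education (control condition) about common infections". On the panel: "All clinician prescribers within primary care clinics will have access to these order panels, however the order panel will vary in functionality" by arm.
- **Control panel, first description.** "For control clinics, the order panel will include diagnosis and drug name only", with the prescriber left to set the duration.
- **Control panel, second description** (the later paragraph on the education session). "Control order panel will include only antibiotic names and doses".
- **Intervention clinics alone.** The panel with prefilled short durations, a free-text justification when the default is overridden, and visual reminders in the clinic.

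The hypothesis in Section 2.1 is that short courses will be more frequent in clinics with the intervention than in control clinics. It does not use the term education-only.

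**The concern.** The objective names the comparator, and the comparator determines what the result will be said to show. If the package includes an order panel and control clinics also have one, any effect of having a panel is present in both arms and, if effects add, drops out of the difference. The trial would then estimate what default duration, justification and reminders add to education plus a panel without durations. That is not the whole package against education alone. A network with no panel at all could misread the result as its expected gain from adopting everything.

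The two descriptions of the control panel add to the doubt. Each uses the word only. One lists diagnosis and omits dose, and the other lists dose and omits diagnosis. If the control panel had no diagnosis step, the arms might differ in diagnosis prompting as well as in the default. That would matter because the definition of a short course depends on the diagnosis.

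**Working it through.** **1. The stated figure.** Section 6.1 gives n = 300 per arm, control rate p1 = 0.53, difference 0.1124 (so p2 = 0.6424) and alpha 0.05. Two-sided testing is assumed, since the section does not say, and encounters are treated as independent.

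- Mean rate: (0.53 + 0.6424)/2 = 0.5862.
- Null standard error: √(2 × 0.5862 × 0.4138/300) = 0.04021; times 1.96 = 0.0788.
- Alternative standard error: √((0.53 × 0.47 + 0.6424 × 0.3576)/300) = 0.03995.
- Power: Φ((0.1124 − 0.0788)/0.03995) = Φ(0.84) = 0.7997.

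Solving the same formula for 80% power gives 11.244 points, so the stated 11.24 reproduces. No term depends on what the control is called. Whether independence is a fair assumption under randomization by region is a separate matter.

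**2. Which elements each arm receives, from Sections 1.0 and 2.1.**

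| Element | Intervention | Control |
|---|---|---|
| Baseline education | yes | yes |
| An order panel | yes | yes |
| Default short duration in the panel | yes | no |
| Justification on override | yes | no |
| Visual reminders | yes | no |

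The two shared rows are not what the protocol calls the behavioral economics package. Section 1.0 defines the panel component by its default duration, and Section 2.1 restricts that version to intervention clinics. By the protocol's own definition, control clinics receive no component of the package. Education-only is then loose shorthand for a control without behavioral economics strategies.

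**3. The two control-panel descriptions side by side.**

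| Field | First description | Second description |
|---|---|---|
| Diagnosis | listed | not listed |
| Drug name | listed | listed |
| Dose | not listed | listed |
| Duration | absent | absent |

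They disagree on diagnosis and dose and agree on duration. Each is written to contrast with the intervention panel's duration field; the text that follows each one concerns duration. Section 2.1 gives a single trigger for the panel, a typed drug name or a typed diagnosis, without distinguishing arms. That makes it unlikely that the second description was meant to remove diagnosis from the control panel. Under Section 2.3 the analysis takes diagnosis codes from the encounter record in both arms, and Section 15.0 takes drainage status from procedure data, so the panel's display is not the source for classifying a course as short.

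**4. Could a panel effect be sized?** The documents give none. As a pure assumption, hold the intervention rate at 64.24% and let the control panel raise the 53% control rate by 0, 1, 2, 3 or 5 points. Power by the formula in step 1 is then 80.0%, 72.4%, 63.6%, 54.0% or 34.7%. Any such loss would come from giving control clinics a panel. Renaming the control would not recover it.

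**The case for a change.** The strongest case for a change is that the objective is the sentence readers carry away. No arm receives education alone, so a report of package against education-only would claim a comparison that was not made, and a reader cannot tell from the text exactly which control panel was built. The summary also omits the visual reminders that Section 2.1 lists. The cost of correction is a few words.

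Much of this stands as description. The label is imprecise, the two panel descriptions conflict, and the intervention components are listed unevenly. The inference that the primary contrast cannot be estimated does not stand. Section 2.1 discloses the panel in both arms, and the hypothesis concerns intervention and control clinics as defined there. Holding the ordering tool constant arguably isolates the behavioral strategies better than a control with no panel would. The suggestion that only one arm is prompted for a diagnosis rests on the less natural reading of one sentence. Nothing in the documents supports a particular size for the panel's own effect.

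**Conclusion.** This is a clerical imprecision, and it calls for no change to the plan. Followed as written, the protocol yields the same arms, encounters, outcome, estimate and power whether the control is called education-only or education plus an order panel without durations. The effect on the stated figures is nil: 11.24 points at about 80% power reproduces and does not depend on the label. The comparison tests default duration, justification and reminders together, on a background of education and a panel in both arms. Section 2.1 already gives an analyst or author enough to report it that way.

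The conclusion assumes that the control panel as built carried no default duration, on which both descriptions agree, and that diagnosis and drainage for the outcome come from the encounter record in both arms, as Sections 2.3 and 15.0 indicate. Aligning the wording would be good housekeeping but would alter no result.

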2.0 Methods

2.1 The 14 NCH primary care clinics will be distributed into five geographic “regions.” Regions will be randomly assigned to the intervention condition or control condition. A region refers to a localized geographical zone within the greater Columbus area in which a NCH primary care pediatrician restricts her/his practice to a small number of clinics. All clinics (intervention and control) will receive baseline education regarding prescribing guidelines and release of a new Epic order panel. All 14 clinics will receive baseline education (control condition) about common infections and local and national guidelines for antibiotic choice and duration of treatment. Clinician prescribers will also be instructed about the presence of a new Epic order panel. The SSTI order panel will present itself when a clinician prescriber types in either a

NATIONWIDE CHILDREN'S HOSPITAL
SHORT PROTOCOL (Waiver of Consent or Verbal Consent)

PROTOCOL TITLE: SSTI BE in PC

preferred drug name (cephalexin, clindamycin, TMP-SMX) or diagnosis (cellulitis, impetigo, etc). All clinician prescribers within primary care clinics will have access to these order panels, however the order panel will vary in functionality based on control vs intervention clinic. For control clinics, the order panel will include diagnosis and drug name only- antibiotic duration must be then determined by the clinician prescriber at the time of the visit. Within intervention clinics, the Epic order panel will include prepopulated default “short” duration antibiotic days based on diagnosis chosen. Short antibiotic duration is defined as 5 days or fewer for cellulitis or drained abscess and 7 days for impetigo or undrained abscess. This- full functionality, default short duration- order panel will only be released to intervention clinics. We hypothesize that clinics with the intervention will have higher rates of short course antibiotics for SSTI versus control clinics. In addition, those randomized to the study intervention sites will receive the following behavioral economic strategies: (1) Epic order panel for cellulitis, impetigo, and abscess with prepopulated duration fields regarding prescriptions; (2) accountable justifications to document reasoning (in a free text field) when the default duration is overridden; and (3) visual reminders placed in intervention clinics about the available Epic order panel. Encounter data for specific diagnosis codes with skin and soft tissue infections will then be collected and analyzed to include clinic location, patient demographics and presenting clinical characteristics, diagnoses, antibiotic treatment (name, dose, duration), and clinician prescriber names. Prescriptions for systemic antibiotics for the selected diagnoses will be reviewed and analyzed for rates of long and short course antibiotics. Rates of short and long antibiotics will be compared between the intervention and control groups.

An education session (virtual via department meeting) will be provided at start of study to all clinics. The education session will include a succinct overview of current local and national treatment guidelines for SSTI. These guidelines include the 5-day and 7-day recommended durations mentioned in the previous paragraph. All clinics will be informed of the presence of order panel for diagnoses of interest. The information included in the order panel will vary based on whether a clinic resides in the control or intervention group. Control order panel will include only antibiotic names and doses. Intervention order panel will include default duration based on SSTI diagnosis.

For the secondary objective, patient demographic and clinical characteristics and clinician prescriber characteristics will be analyzed to determine which factors impact short versus long antibiotic treatment duration.

NATIONWIDE CHILDREN'S HOSPITAL
SHORT PROTOCOL (Waiver of Consent or Verbal Consent)

PROTOCOL TITLE: SSTI BE in PC

2.2 Clinician prescribers will provide prescriptions to patients for SSTI based on previously published national and local guidelines as well as prescriber preference/practice. Patients in primary care clinics receiving antibiotic prescriptions for SSTI will also serve as study subjects. No additional risks are incurred by subjects (clinician prescribers and patients) by participation in this study. For clinician prescribers in clinics randomized to the intervention group, use of the Epic order panel will be optional. Patients receiving care for SSTI in the NCH primary care clinics will receive no more than minimal risks as clinician prescribers will be providing treatment for SSTI as previously done, except for the optional use of the order panel. The study involves no direct interaction with clinic patients, and implementation of the BE interventions does not increase risks associated with treatment of SSTI.

2.3 This study will utilize an existing retrospective and ongoing prospective dataset created by Quality Improvement Services for the routine activities of the NCH Antimicrobial Stewardship Program. All data is queried from Epic. Clinician prescriber and patient information for encounters with the following diagnosis codes will be obtained: A46 (cellulitis), L03 (cellulitis and acute lymphangitis), J34 or L02 (abscess, furuncle), or L01 (impetigo). Data from encounters for the aforementioned diagnoses will be collected if patients are 3 months of age (at minimum) and prescribed enteral antibiotics. The following encounters will be excluded: animal or human bite wound, immunocompromised patients, a concomitant non-SSTI diagnosis treated with an antibiotic during the same encounter, or an SSTI visit in the 7 days prior to the index encounter. Patient data collected will encompass patient demographics, clinical signs and symptoms, diagnosis codes, available culture data, antibiotic treatment (name, route, and duration), and clinician prescriber name.

Clinician prescriber characteristics and demographics will be obtained from NCH website/intranet by manual extraction by primary investigators.

2.4 Source records include the aforementioned monthly report from QIS (extracted from Epic) and manual chart review.

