6.0 Number of Subjects (Records)

- 6.1 Since this study includes patient encounters throughout the NCH primary care network, all clinicians who see patients in the NCH primary care clinics will be included. Currently, there are 98 clinician prescribers who will be included within the study. New clinicians who are hired during the study will be included as well. Based on retrospective data of the previous 12 months, there were approximately 1000 encounters (including information about the patients for these encounters) with just over 600 systemic antibiotic prescriptions. Based on this data, we expect there will be a similar number of encounters and antibiotic prescriptions which would meet inclusion for this study. Assuming an encounter/prescription sample size of 600 (300 intervention, 300 control), power analysis demonstrated greater than 80% power to detect an 11.24% or greater absolute difference in the rate of short-course prescriptions between intervention and control, with a 5% type I error rate (alpha= 0.05), assuming a baseline 53% short-course prescription rate in the control group.

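### Does the bare 7-day figure in the short-course definition leave courses under 7 days for impetigo or undrained abscess unclassified?

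*Protocol*

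**What the plan says.** Protocol Section 2.1 gives the only definition of the outcome: "Short antibiotic duration is defined as 5 days or fewer for cellulitis or drained abscess and 7 days for impetigo or undrained abscess". It then states how the outcome is used: "Rates of short and long antibiotics will be compared between the intervention and control groups". Long is not defined separately.

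The same section describes the two order panels. In intervention clinics "the Epic order panel will include prepopulated default “short” duration antibiotic days based on diagnosis chosen". In control clinics "antibiotic duration must be then determined by the clinician prescriber at the time of the visit". Section 2.2 adds, for clinicians in the intervention clinics, that "use of the Epic order panel will be optional".

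The day figures come up once more, in the Section 2.1 account of the education session given to all clinics: "These guidelines include the 5-day and 7-day recommended durations mentioned in the previous paragraph". In the Confidential Health Information part of Section 15.0, drainage data are said to be needed to judge whether the duration agreed with guidelines, without a cut-off.

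Section 6.1 bases the power statement on the same rate, "assuming a baseline 53% short-course prescription rate in the control group", with 300 prescriptions per arm and a detectable difference of 11.24 points.

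**The concern.** One sentence uses two forms of threshold. For cellulitis and drained abscess (the 5-day group) it sets an upper limit. For impetigo and undrained abscess (the 7-day group) it gives a single number. Read word for word, a prescription of fewer than 7 days in the second group fails the definition of short, and nothing else in the protocol says where it goes.

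The stake is the main comparison. Only the intervention panel pre-fills a duration, and overriding it requires a written reason. If the default draws courses towards exactly 7 days, courses under 7 days could become rarer in the intervention arm than in control. Scoring them as long would then lower the control rate more than the intervention rate, and part of an apparent effect would come from the counting rule. It is also not stated which rule produced the 53% baseline.

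**Working it through.** **1. The plan's own figure.** Inputs from Section 6.1: n = 300 per arm, control rate 0.53, difference 0.1124 (so intervention rate 0.6424), alpha 0.05, taken as two-sided, no clustering term.

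- Mean rate = (0.53 + 0.6424)/2 = 0.5862.
- Standard error under no difference = sqrt(2 × 0.5862 × 0.4138/300) = 0.0402.
- Standard error under the alternative = sqrt((0.53 × 0.47 + 0.6424 × 0.3576)/300) = 0.0400.
- Power = Φ((0.1124 − 1.96 × 0.0402)/0.0400) = 79.97%. With the unpooled standard error throughout it is 80.3%.
- Solving the pooled formula for 80% power gives a detectable difference of 11.244 points.

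The stated figure reproduces. It does not depend on how 7 days is read, except through the 53%.

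**2. What the wording supports.**

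- *Two classes only.* The protocol compares short with long and has no third class. On the literal reading a 5-day course in the 7-day group would have to be long while a 7-day course for the same diagnosis is short. That reverses the plain meaning of the labels, in a trial titled "Decreasing Antibiotic Duration for Skin and Soft Tissue Infections in Pediatric Primary Care".
- *The education paragraph.* It drops the upper-limit wording from both figures, including the 5-day one, where an upper limit is certain. A bare number in this document can therefore stand for a limit, and the two figures are treated alike.
- *Panel default.* The definition follows directly on the description of the pre-filled field, so 7 might be read as the default value. But a pre-filled field holds one number, and the 5-day half of the sentence is a range. The sentence is defining a class of durations.
- *Long.* Once short is an upper limit in both groups, long is its complement and needs no definition of its own.

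**3. What the literal reading would do if it were used.** Let s be the share of prescriptions in the 7-day group (taken as equal in the arms) and q the fraction of those under 7 days. Relative to an upper limit, the literal rule lowers an arm's rate by s × q, so the arm difference changes by s × (q_control − q_intervention). The documents give neither s nor q, so every value below is an assumption.

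| s | q control | q intervention | Shift in arm difference |
|---|---|---|---|
| any | equal | equal | 0 |
| 40% | 5% | 3% | 0.4 × 0.02 = 0.8 points |
| 40% | 12.5% | 3% | 0.4 × 0.095 = 3.8 points |
| 50% | 20% | 1% | 0.5 × 0.19 = 9.5 points |
| 50% | 1% | 20% | 0.5 × (−0.19) = −9.5 points |

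The size and the sign both come from the assumed inputs.

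**4. Effect on the sample-size statement.** The control rate differs between the readings by s × q_control: 0.3 × 0.05 = 1.5 points, 0.4 × 0.125 = 5.0 points, 0.5 × 0.20 = 10 points. If 53% came from the literal rule, the upper-limit rate would be 54.5%, 58% or 63%. The detectable difference at 80% power would then be 11.18, 10.99 or 10.62 points, against 11.24.

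**The case for a change.** The strongest case for a change is that the protocol does not leave this rule to a later document. It defines the outcome and does so unevenly, and an SAP that copied the sentence would inherit the fault. The wording about agreement with guidelines in Section 15.0 could suit an exact-match rule. The default acts in one arm only, so any misclassification need not balance. A repair would cost a few words and a recheck of the retrospective rate.

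Part of this stands. The asymmetry is real, no sentence classifies the shorter courses, and the rule behind the 53% is not stated. The rest is weaker. An exact-match rule does not fit the 5-day group, where courses shorter than the recommended figure plainly count as short, and nothing suggests that the two groups were meant to follow different logic. Nor does anything suggest one rule for the baseline and another for the trial, or different rules by arm. Distortion needs two things together: that courses under 7 days are scored as long, and that they are a different fraction of prescriptions in the two arms. The first is the unlikely reading. The second is possible but undocumented, since both arms receive the same education and panel use is optional. Reporting days prescribed by arm would be an added analysis that corrects no error.

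**Conclusion.** No change to the plan follows. The missing upper-limit wording is a clerical slip, and the two-class outcome and the aim of the trial settle how it will be coded: short is at or below the group's figure, long is above it. That is a statement about counting the outcome and takes no view on what should be prescribed. Writing the rule out would record what is very probably meant, without altering the result.

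No effect on the arm difference can be put in figures from the documents. It is zero if the upper limit is used in both arms. It is also zero under the literal rule if courses under 7 days in the 7-day group form the same fraction of prescriptions in each arm. The power statement reproduces, and the detectable difference falls by at most 11.24 − 10.62 = 0.62 points over the assumed range. The conclusion rests on the upper-limit reading, which the protocol implies but does not state, and on the 53% having been counted by the same rule, which nothing in the protocol contradicts.

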8.0 Withdrawal of Subjects

- 8.1 Because this study will randomize at the level of a group of clinics (regions) with minimal risk to clinician prescribers and no direct interaction with patients, we are requesting a waiver of informed consent. Thus, clinician prescribers will not be able to withdraw from the research except by ending their employment in the NCH PCCs as standard of care clinicians. The interventions in the study include education and order panels, which clinicians are not forced to use. Encounter data from each clinician will be analyzed by quadrant. Clinician prescribers who end their employment in the NCH PCCs during the study, the data for their SSTI encounters will be continue to be included.

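### Does the comparison of short-course rates between arms go wrong by giving the prior-year prescriptions no stated role?

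*Protocol*

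**What the plan says.** Section 2.1 of the Protocol groups 14 clinics into five regions: "Regions will be randomly assigned to the intervention condition or control condition". It states no matching, stratification or constraint on earlier prescribing. The follow-up data are described next: "Encounter data for specific diagnosis codes with skin and soft tissue infections will then be collected and analyzed to include clinic location". The arm comparison is one sentence: "Rates of short and long antibiotics will be compared between the intervention and control groups". No test, model, covariate list or unit of analysis is attached to it.

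Section 2.3 states the source: "This study will utilize an existing retrospective and ongoing prospective dataset created by Quality Improvement Services". Section 2.4 adds: "Source records include the aforementioned monthly report from QIS (extracted from Epic) and manual chart review".

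Section 6.1 reports about 1000 encounters in the previous 12 months "with just over 600 systemic antibiotic prescriptions" and uses them to project the study's size. The power statement follows: "Assuming an encounter/prescription sample size of 600 (300 intervention, 300 control"), more than 80% power for 11.24 points, alpha 0.05, and a control rate of 53% that is called a baseline rate but given no source.

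Section 8.1 says: "Encounter data from each clinician will be analyzed by quadrant". Section 15.0 (Confidential Health Information, item 2.0) foresees analysis by provider and by clinic. These two places speak of the level of analysis, not of covariates.

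**The concern.** Randomising five regions balances them only on average. A 2 v 3 split has ten possible allocations and one of them is realised. If regions differ persistently in how often they prescribe short courses, the arms may start apart, and a comparison of follow-up rates alone cannot separate that gap from an effect. The study appears to hold about a year of earlier prescriptions from the same clinics, which would show the gap and might allow adjustment for it. Reading section 2.1 beside sections 2.3 and 6.1, one could conclude that the plan leaves this protection unused, and that part of an 11.24-point result could be regional history.

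**Working it through.** **1. The plan's own figure.** Inputs from section 6.1: 300 per arm, control rate 0.53, difference 0.1124, alpha 0.05 (taken as two-sided).
- Mean rate = (0.53 + 0.6424)/2 = 0.5862. Null SE = sqrt(2 × 0.5862 × 0.4138/300) = 0.0402.
- Alternative SE = sqrt((0.53 × 0.47 + 0.6424 × 0.3576)/300) = 0.0400.
- Power = Φ((0.1124 − 1.96 × 0.0402)/0.0400) = 0.7997. Solving for 80% gives 11.24 points.

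The figure reproduces as a calculation for independent prescriptions. It has no region term; that is a separate matter from baseline data.

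**2. The chance gap.** Assumptions, none in the document: a 2 v 3 split, 120 prescriptions per region and period (600/5), and the ICC. Between-region SD s = sqrt(ICC × 0.53 × 0.47). SD of the arm gap = s × sqrt(1/2 + 1/3). Mean absolute gap = 0.798 × that SD.

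| ICC | s (points) | SD of gap | Mean absolute gap | P(gap > 5.62) | P(gap > 11.24) |
|---|---|---|---|---|---|
| 0.005 | 3.5 | 3.2 | 2.6 | 8% | 0.05% |
| 0.01 | 5.0 | 4.6 | 3.6 | 22% | 1.4% |
| 0.02 | 7.1 | 6.4 | 5.1 | 38% | 8% |
| 0.05 | 11.2 | 10.2 | 8.1 | 58% | 27% |

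At ICC 0 the gap is zero. These figures express between-region variance with five units. A region-level analysis of follow-up rates carries that variance in its standard error. They are therefore not the cost of leaving out baseline data.

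**3. What baseline data would buy at region level.** Let r be the correlation of a region's true rate from one year to the next (assumed). The correlation of the observed rates is ρ = r·s²/(s² + 0.2491/120).
- Follow-up only: SE = sqrt((s² + 0.2491/120) × 5/6), 3 df, critical t 3.18.
- Change from baseline: SE = follow-up SE × sqrt(2(1 − ρ)), 3 df. It is smaller only if ρ exceeds 0.5.
- Analysis of covariance: follow-up SE × sqrt(1 − ρ²) if the slope were known. Estimating the slope on 3 within-arm df multiplies the variance on average by 1 + 1/(3 − 2) = 2. It leaves 2 df, critical t 4.30.

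Example, ICC 0.01 and r = 0.8: ρ = 0.8 × 0.00249/(0.00249 + 0.00208) = 0.44. Follow-up SE is 6.2 points. Change SE is 6.2 × sqrt(2 × 0.56) = 6.6.

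Median half-width of the 95% interval in points, from 100,000 simulated trials per row (normal approximation):

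| r | ICC | ρ | Follow-up only | Change | Covariance |
|---|---|---|---|---|---|
| 0.8 | 0.005 | 0.30 | 14.9 | 17.6 | 21.3 |
| 0.8 | 0.01 | 0.44 | 17.4 | 18.5 | 23.5 |
| 0.8 | 0.02 | 0.56 | 21.6 | 20.2 | 26.7 |
| 0.8 | 0.05 | 0.69 | 31.1 | 24.7 | 33.9 |
| 0.5 | 0.005 | 0.19 | 14.9 | 18.9 | 21.8 |
| 0.5 | 0.01 | 0.27 | 17.4 | 21.0 | 25.0 |
| 0.5 | 0.02 | 0.35 | 21.7 | 24.6 | 30.3 |
| 0.5 | 0.05 | 0.43 | 31.1 | 33.2 | 42.1 |

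The follow-up comparison on 3 df held its type I error at about 5% in every row. Covariance adjustment widened the interval in all eight rows, and change from baseline in six.

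**4. A mixed model on both periods.** SD of the estimate in points, unadjusted v adjusted, for ICC 0.005, 0.01, 0.02, 0.05:
- r = 0.8: 5.2 v 5.2, 6.1 v 5.8, 7.6 v 6.7, 11.0 v 8.5.
- r = 0.5: 5.2 v 5.3, 6.1 v 6.2, 7.6 v 7.6, 11.0 v 10.5.

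At r = 0.8 over ICC 0 to 0.05, its type I error was 0.1% to 1.8% with a flat 3 df and 4% to 12% with no small-sample correction, against a nominal 5%.

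**5. The text.** Section 2.1 says that rates will be compared and stops there. A model adjusted for the earlier rate is also a comparison of rates between groups. Section 2.3 commits the study to a dataset with a retrospective part and does not restrict its use. A baseline-adjusted analysis in the statistical analysis plan would contradict neither.

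**The case for a change.** The strongest case is that the protocol itself fixes the allocation, the data source and the comparison, and that with ten possible splits one bad draw matters whatever holds on average. With assumed true regional rates of 45, 49, 53, 57 and 61%, four of the ten splits put the arms at least 6.7 points apart with no effect at all; the largest gap is 10 points. Regions are defined by where pediatricians confine their practice (2.1), and prescribing follows personal preference (2.2), so lasting regional differences are plausible. Where they are large and persistent, the mixed model does help: the SD falls from 7.6 to 6.7 points at ICC 0.02 and from 11.0 to 8.5 at 0.05, both at correlation 0.8.

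The risk of a chance gap stands, and so does the value of showing readers the baseline rates by region and arm. The step from there to a flaw in the plan does not. The gain depends on an ICC and a persistence that the document does not give, and education and a new order panel for all clinics at the start could weaken persistence. That the retrospective part covers the same 12 months as section 6.1 is a reasonable inference, not a statement. The table would also have a cost: the short-course definition needs drainage status for abscesses, and if abscesses are 20% to 50% of about 600 prescriptions (assumed), that is 120 to 300 records.

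**Conclusion.** The concern does not hold. Section 2.1 leaves open how rates are compared and excludes no baseline term. Whether to adjust for prior-year rates is a choice of model that a protocol commonly leaves to the statistical analysis plan, so silence on it is neither an error nor a contradiction. The follow-up comparison is unbiased over randomisations.

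The chance gap of 2.6 to 8.1 points is correctly calculated but measures the effect of having five regions, under an assumed ICC of 0.005 to 0.05 and a 2 v 3 split. Adjustment is a trade-off: at ICC 0.01 and correlation 0.8 the region-level half-width rises from 17.4 to 18.5 or 23.5 points. A clear gain needs both an ICC of at least 0.02 and persistence near 0.8. The absence of clustering from the power figure in section 6.1 is a different question and is not settled here. What remains is a reporting suggestion.
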